6.2 Treatment Regimens

Approximately 30 subjects will be randomized to self-administer double-blinded study medication by subcutaneous injection at a dose of 10 mg BMS-986036 daily, 20 mg BMS-986036 weekly, or placebo daily for 16 weeks. The following table shows the total dose and number of subcutaneous injections per dose for each treatment group.

Table 6.2-1: Treatment Administration

Treatment		Solution Strength	Number and volume of subcutaneous injections	
			Day 1 ^a of each treatment week	Days 2 - 7 of each treatment week
Lead-in phase	Placebo QD	N/A	2 x 1 mL	1 x 1 mL, daily
A	BMS-986036 10 mg QD	10 mg/ml	2 x 1 mL ^b	1 x 1 mL, daily
B	BMS-986036 20 mg QW	10 mg/ml	2 x 1 mL	1 x 1 mL, daily ^c
C	Placebo QD	N/A	2 x 1 mL	1 x 1 mL, daily

^a For all treatments, on Day 1 of each treatment week, two injections are administered concurrently, in the morning.

^b For treatment A, on Day 1 of each treatment week, the 2 injections consist of 1 active and 1 placebo, to maintain the blind between daily and weekly treatment arms.

^c For treatment B, on Days 2-7 of each treatment week, the injection is placebo, to maintain the blind between daily and weekly treatment arms.

All analyses will be based on actual treatment regimens (“as treated”). Observations on safety parameters will be assigned to the most recent treatment regimen received.

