4 STUDY DRUG

Study drug includes both Investigational [Medicinal] Product (IP/IMP) and Non-investigational [Medicinal] Product (Non-IP/Non-IMP) and can consist of the following:

- All products, active or placebo, being tested or used as a comparator in a clinical trial.
- Study required premedication, and
- Other drugs administered as part of the study that are critical to claims of efficacy (e.g., background therapy, rescue medications)
- Diagnostic agents: given as part of the protocol requirements must also be included in the dosing data collection.

BMS-986036 will be provided as a blinded solution for subcutaneous injection. Randomized subjects will self-administer double-blind treatment, once daily for 16 weeks, in an outpatient setting. Blinded treatment is supplied in Kits. Each Kit contains 8 vials, to support 1 week of treatment. 2 vials are provided for use on Day 1 of each week, and 1 vial is provided for use each day, on Days 2-7.

Once-daily treatment will consist of subcutaneous injection(s) administered in the abdomen. Subjects will be trained to rotate injection sites relative to the umbilicus. The time of dose administration will be called “0” hour, with regard to pre- and postdose clinical planned events. On clinic visit days, the morning injections are administered at the clinic, at a time determined by the Investigator to coordinate with the pre- and post-dose protocol specified clinical events scheduled for that clinic visit day. Treatment administration is described in Table 4-1.

Table 4-1: Treatment Administration

Treatment		Solution Strength	Number and volume of subcutaneous injections	
			Day 1 ^a of each treatment week	Days 2 - 7 of each treatment week
Lead-in phase	Placebo QD	N/A	2 x 1 mL	1 x 1 mL, daily
A	BMS-986036 10 mg QD	10 mg/ml	2 x 1 mL ^b	1 x 1 mL, daily
B	BMS-986036 20 mg QW	10 mg/ml	2 x 1 mL	1 x 1 mL, daily ^c
C	Placebo QD	N/A	2 x 1 mL	1 x 1 mL, daily

^a For all treatments, on Day 1 of each treatment week, two injections are administered concurrently, in the morning.

^b For treatment A, on Day 1 of each treatment week, the 2 injections consist of 1 active and 1 placebo, to maintain the blind between daily and weekly treatment arms.

^c For treatment B, on Days 2-7 of each treatment week, the injection is placebo, to maintain the blind between daily and weekly treatment arms.

Product description and storage information is described in [Table 4-2](#).

Table 4-2: Study Drugs for MB130045

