Patient education: subcutaneous injection and diary usage	X								The Investigator will review subject diary, placebo compliance, and assess self-injection skills on Day 1 BEFORE randomizing the subject.
IVRS call	X	X	X	X	X	X	X	X	IVRS call to be conducted on the day of each subject visit
Randomize	X								Predose on Day 1.
Safety Assessments									
Inclusion/Exclusion Criteria	X								Predose on Day 1.
Physical Examination (PE)	X						X	X	Predose on Day 1. Injection site reactions (as measured by the Draize Scale for erythema and edema (see Section 5.3.3))
Targeted PE		X	X	X	X	X			See note in screening procedures.
Physical Measurements	X	X	X	X	X	X	X	X	Weight, BMI and waist circumference measurement. Weight must be recorded using a calibrated scale. Predose on Day 1.
Vital Signs	X	X	X	X	X	X	X	X	See note in screening procedures.
Electrocardiogram (ECGs)	X						X	X	See note in screening procedures, or as clinically indicated.
Laboratory Tests (hematology, clinical chemistry, urinalysis, INR)	X	X	X	X	X	X	X	X	Pre-dose on Day 1. See note in screening procedures and Section 5.3.2 .
Pregnancy Testing	X		X		X	X	X	X	Female subjects of child bearing potential. Urine pregnancy testing performed at all specified visits, with a reflex to serum pregnancy testing if urine pregnancy testing is positive.
Dual-emission X-ray Absorptiometry (DXA)							X	X	Window +/- 1 week Bone imaging (hip and lumbar spine) at all imaging facilities.
Adverse Event Reporting									
Monitor for Non-Serious Adverse Events	X	X	X	X	X	X	X	X	Day 1 assessment occurs after study drug administration.
Monitor for Serious Adverse Events	X	X	X	X	X	X	X	X	See note in screening procedures.
Efficacy Assessments									
MRI					X		X	X	MRI should be conducted within +/- 1 week. At early termination, MRI conducted only if subject received ≥ 6 weeks of study drug and was ≥ 1 month from previous MRI.

Table 5.1-2: On Treatment Procedural Outline (MB130045)

Procedure	D 1	D 15	D 29	D 43	D 57	D 86	End of Treatment D 112	Early Termination Visit ^a	Notes
Pharmacokinetic (PK) Assessments									
PK Sampling	See Table 5.5.1-1								
Immunogenicity testing	See Table 5.5.1-1								Refer to Section 5.7
[REDACTED]									[REDACTED]
[REDACTED]									[REDACTED]
Clinical Drug Supplies									
Review injection technique	X								
Dispense Study Drug	X	X	X	X	X	X			Supplied by BMS.
Blinded drug administration	X	X	X	X	X	X	X		Blinded treatment will be administered at the site on clinic visit days.

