2.2 Treatment Assignment

During the Screening visit, the investigative site will call into the enrollment option of the IVRS designated by BMS for assignment of a 5-digit subject number that will be unique across all sites. Enrolled subjects, including those not dosed, will be assigned sequential subject numbers starting with 00001, eg, 00001, 00002, 00003.... 00010. The patient identification number (PID) will ultimately be comprised of the site number and subject number. For example, the first subject screened (ie, enrolled) at site number 1, will have a PID of 0001 00001. Once it is determined that the subject meets the eligibility criteria following the Screening visit, the investigative site will call the IVRS to randomize the subject into the open dose panel.

At the time of entry into the lead-in period (Day -7 visit), the site will call IVRS in order for the lead-in medication to be assigned and dispensed. Subjects who successfully complete the lead-in period and meet the criteria for entry into the treatment period, will be randomly assigned by the IVRS to one of the following 3 double-blind treatment groups in a 1:1:1 ratio:

- BMS-986036 10 mg once daily (QD)
- BMS-986036 20 mg once weekly (QW)
- Placebo QD

Randomization will be stratified based upon diagnosis of Type 2 diabetes mellitus (yes vs. no).

The two strata for randomization are defined as follows:

- Strata 1: Diabetes Mellitus - Yes
- Strata 2: Diabetes Mellitus - No

Randomized subjects who discontinue will not be replaced.

Randomization schedules for both subject treatment and containers will be generated and kept by Bristol- Myers Squibb and stored in a secure location with restricted access.

At all study visits when study medication is dispensed, each subject will be assigned a kit number by the IVRS. Kit numbers will be assigned randomly and will correspond to the numbers printed on the packages and kits containing study drug. Kit numbers will be recorded on the appropriate eCRFs. The IVRS will be available 24 hours per day, 7 days per week.

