6.3 Populations for Analyses

- All Enrolled Subjects, defined as all subjects who signed an informed consent;
- All lead-in subjects, defined as all subjects who have received at least one dose of placebo during the placebo lead-in period;
- All Randomized Subjects, defined as all subjects who are randomized to a treatment during the treatment period;
- All Treated Subjects, defined as all subjects who have received at least one dose of study treatment during the treatment period;
- Pharmacokinetic Population, defined as all subjects who receive any study medication and have any available concentration-time data. Additionally, the Evaluable PK Population is defined as subjects who have adequate PK profiles.

All available derived PK parameter values will be included in the PK data set and reported, but only subjects with adequate PK profiles will be included in the summary statistics and statistical analysis.

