7.4 Extent of Exposure

Extent of exposure for 16-week double blinded treatment period will be summarized for all treated subjects, presenting the numbers and percentage of subjects with an extent of exposure within the following day ranges by treatment group: 1 to 15, 16 to 29, 30 to 43, 44 to 57, 58 to 86, 87 to 112 and > 112. Also the mean, SD, median and range of the extent of exposure to blinded treatment will be presented by treatment group. Study drug administration, randomization schedule will be documented as per subject listings. Any non-study medications taken by subjects, any conducted non-study medical treatment procedures, and any utilized non-study diagnostic procedures will also be listed.

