7.5 Efficacy

To evaluate the effect of BMS-986036 on change in hepatic fat fraction (%) by MRI in subjects with biopsy-proven NASH after 16 weeks of treatment, a longitudinal repeated measures analysis will be used to analyze the change in hepatic fat fraction (%) from baseline to Week 16 in the treated population who have both a baseline and at least one post-baseline measurement. The model will include treatment group, week and treatment-by-week interactions as main effects and baseline hepatic fat fraction (%) and baseline diabetic status as covariates. An unstructured covariance matrix will be used to represent the correlation of the repeated measures within each subject. The model will provide point estimates, standard errors and 2-sided 90% confidence intervals for mean change from baseline at all time points within and between treatments. P-values will be calculated to compare the treatment effect in each of two BMS-986036 (10 mg daily and 20 mg weekly) treatment groups to that in the placebo treatment group at Week 16. Each treatment group comparison will be performed at a one-sided 0.05 significance level. No adjustment will be made for multiplicity.

Summary statistics will be tabulated for all treated subjects by treatment, study day for hepatic fat fraction (%) with corresponding change from baseline. Plot of mean profile over time will also be provided for hepatic fat fraction (%) by treatment. In addition, the descriptive statistics for hepatic fat fraction (%) will be summarized by baseline NASH CRN fibrosis staging (1, 2, 3), type 2 diabetes mellitus (yes, no), NAS (NAFLD activity score) and fatty liver index.

Two sensitivity analyses will be performed in the longitudinal repeated measure analysis.

- For patients without measurement at week 16 for hepatic fat fraction (%), last observation for hepatic fat fraction (%) measured on or after Day 86 will be carried forward to be the value at week 16.
- Baseline NASH CRN fibrosis staging and the treatment-by-baseline diabetic status interactions will be included in the model. The effect of BMS-986036 on the change in hepatic fat fraction (%) from baseline to week 16 within each stratum will be analyzed.

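### SAP 6.2 applies an as-treated rule to all analyses with no exception for efficacy, and no visible text classifies subjects by randomised arm in the primary Week 16 comparison

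*SAP*

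**What the plan says.** SAP Section 6.2, below the treatment administration table, gives the classification rule: "All analyses will be based on actual treatment regimens", glossed there as an as-treated approach. The next sentence adds: "Observations on safety parameters will be assigned to the most recent treatment regimen received". That sentence concerns safety parameters only.

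SAP Section 7.5 describes the primary analysis, a repeated measures model in treated subjects with a baseline and at least one post-baseline measurement: "The model will include treatment group, week and treatment-by-week interactions as main effects". Protocol Section 8.4.2 describes the same model and analysis set. Neither section says whether treatment group means the arm assigned or the treatment received.

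SAP Section 2.2 says subjects are "randomly assigned by the IVRS to one of the following 3 double-blind treatment groups". SAP Section 6.3 defines a randomised set ("All Randomized Subjects, defined as all subjects who are randomized to a treatment during the treatment period"), but no visible efficacy analysis uses it.

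On supply, Protocol Section 4 says "Each Kit contains 8 vials, to support 1 week of treatment". The row "Dispense Study Drug" in Protocol Table 5.1-2 is marked at Days 1, 15, 29, 43, 57 and 86. On traceability, SAP Section 7.4 says "Study drug administration, randomization schedule will be documented as per subject listings".

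**The concern.** The primary test is a randomised comparison of each active arm with placebo. Its validity rests on keeping subjects in the groups that randomisation formed. The usual split is randomised arm for efficacy and treatment received for safety. SAP 6.2 applies the second rule to everything.

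There are two consequences. If a subject received another arm's kits, the literal rule could transfer that subject to another arm in the primary test. If a subject received a mixture of kits, the SAP does not say which arm the subject joins for efficacy, because the most-recent-regimen rule is confined to safety. That choice could then be made after unblinding, with the result in view. Neither sensitivity analysis in SAP 7.5 (carry-forward from Day 86 onward; added fibrosis stage and treatment-by-diabetes interaction) is an as-randomised analysis that would show the difference.

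**Working it through.** **Planned power.** Inputs from SAP Section 5 and Protocol 8.1: 27 per arm, difference 5, SD 7, one-sided alpha 0.05, stated power 82%.
- SE = 7 × √(2/27) = 1.91.
- Noncentrality = 5/1.905 = 2.62. The two-sample t test with 52 df gives power 82.8% (normal approximation 83.6%). The stated 82% is reproduced within rounding and method.

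**Text check.** The places that could set an efficacy exception are:
- SAP 2.2: describes assignment by IVRS, not classification for analysis.
- SAP 6.3 and Protocol 8.2: define who is in each set, not the arm in which a subject is counted.
- SAP 7.2: says relevant deviations will be accounted for in summaries, listings and descriptive analyses; it is silent on classification in the primary test.
- SAP 7.5 and Protocol 8.4.2: use treatment group without defining it.

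None overrides the general sentence in SAP 6.2.

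**Size of a reclassification (assumption: one subject, whole course).** A placebo-randomised subject takes active drug throughout and is counted as active. Take observed as-randomised means of 0 (placebo) and -5 (active), 27 each, so the active sum is -135. Moving a value x gives arms of 28 and 26:

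Difference = (-135 + x)/28 - (0 - x)/26 = (-135 + x)/28 + x/26.

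The subject took active drug, so x is centred on -5.

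| x | Position | Difference | Shift | Shift / 1.905 |
|---|---|---|---|---|
| -5 | active-arm mean | -5.00 - 0.19 = -5.19 | -0.19 | 0.10 SE |
| -12 | 1 SD below | -5.25 - 0.46 = -5.71 | -0.71 | 0.37 SE |
| +2 | 1 SD above | -4.75 + 0.08 = -4.67 | +0.33 | 0.17 SE |

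**How much treatment one error covers.** One wrong weekly kit covers 7 of 112 days. If every kit from one dispensing visit is wrong, the intervals from Days 1, 15, 29, 43, 57 and 86 to Day 112 are 14, 14, 14, 14, 29 and 26 days.

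**Price of the as-randomised rule.** Suppose one placebo subject receives active drug for a fraction f of treatment, with effect assumed proportional to days. The expected as-randomised difference has size 5 × (1 - f/27).

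| Error | f | Difference | Power (t, 52 df) |
|---|---|---|---|
| None | 0 | -5.00 | 82.8% |
| One kit | 7/112 | -4.99 | 82.6% |
| One visit, 14 days | 14/112 | -4.98 | 82.5% |
| One visit, 29 days | 29/112 | -4.95 | 82.1% |
| Whole course | 1 | -4.81 | 80.2% |

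**The case against.** The best counter-reading is that treatment group in SAP 7.5 already means the randomised arm. SAP 2.2 and Protocol 4.5 use that term for the arms assigned by IVRS, whereas the as-treated sentence speaks of regimens. This has force: the defect may be ambiguity and not a settled as-treated primary analysis. It does not remove the problem, because a programmer following an explicit rule for all analyses would use actual treatment. If the sponsor means randomised arm, the sentence in 6.2 contradicts that intention.

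Second, the missing rule may sit elsewhere. SAP 7.2 points to an Appendix 1 that is not visible, parts of the SAP are redacted, and table details are left to a Data Presentation Plan. The absence can therefore be claimed only of the visible text.

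Third, no harm is shown. Kits are assigned by IVRS under double-blinding, so errors should be rare, and the planned listings should make any mismatch traceable. This stands and limits the severity.

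A reader might infer that the rule inflates type I error. The documents do not support that: nothing in them links a kit error to prognosis. A reader might also infer that mixed kits are the likeliest error, but no text gives the frequency of any kind of dispensing error.

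**Conclusion.** The point holds as a minor one. The SAP states an as-treated rule for all analyses, no visible text exempts the primary comparison or its sensitivity analyses, and the efficacy arm of a subject with mixed kits is undefined. The numerical effect is nil unless a subject receives another arm's kits, and the documents give no rate for that. In the whole-course illustration, one reclassified subject moves the estimate by 0.10 SE if typical of the active arm, and by 0.37 or 0.17 SE at 1 SD below or above its mean. These figures rest on the planning values (27 per arm, SD 7, difference -5) and on a simple two-arm comparison without the covariates or the Week 8 measurement.

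It would go too far to say that the trial's primary result is compromised or that the SAP contradicts the protocol. The visible protocol text is silent on classification, and with correct dosing the two approaches give the same answer.

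**What to change.** Keep the general sentence in SAP 6.2 and add an exception to it: *except that hepatic fat fraction efficacy analyses (Section 7.5 and the corresponding interim summaries in Section 7.10) will classify treated subjects by randomised treatment group.*

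Adding an exception is better than replacing the sentence with a list of analyses. A list limited to Section 7.5 efficacy, safety, exposure and PK would leave immunogenicity, the baseline tables and the interim hepatic fat summaries without a rule. The exception also settles the efficacy arm of a subject with mixed kits.

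Run an as-treated efficacy analysis only as a sensitivity analysis, and only if a subject actually received a wrong regimen.

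The cost is one clause in the SAP, made before unblinding. Sample size, alpha, data collection and safety analyses do not change. The only downside is slight dilution if mis-dosing occurs: for one placebo subject on active drug, power falls from 82.8% to no lower than 80.2%.

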6.3 Populations for Analyses

- All Enrolled Subjects, defined as all subjects who signed an informed consent;
- All lead-in subjects, defined as all subjects who have received at least one dose of placebo during the placebo lead-in period;
- All Randomized Subjects, defined as all subjects who are randomized to a treatment during the treatment period;
- All Treated Subjects, defined as all subjects who have received at least one dose of study treatment during the treatment period;
- Pharmacokinetic Population, defined as all subjects who receive any study medication and have any available concentration-time data. Additionally, the Evaluable PK Population is defined as subjects who have adequate PK profiles.

All available derived PK parameter values will be included in the PK data set and reported, but only subjects with adequate PK profiles will be included in the summary statistics and statistical analysis.

7 STATISTICAL ANALYSES

SAS® version 8.2 or higher will be used for statistical analyses, tabulations and graphic presentations. S-Plus® may also be used for graphical presentations.

7.1 General Methods

Descriptive summaries will be presented for continuous variables using number of subjects (N), mean, standard deviation (SD), median, minimum and maximum. Geometric mean and coefficient of variation (%CV) will also be presented for sample plasma concentration-time data and PK parameters. Descriptive summaries for categorical variables will utilize counts and percentages.

Adverse events and medical history will be coded according to the most recent Medical Dictionary for Regulatory Activities (MedDRA) version. Previous and concomitant medications will be coded using the most recent WHO Drug Dictionary version.

Longitudinal summaries of hepatic fat fraction (%), safety and biomarker endpoints use pre-defined visit windows (see [Section 8.1.3](#)).

7.2 Study Conduct

Relevant deviations from the study protocol, unscheduled corresponding unblinding events, protocol amendments and administrative changes will be documented and accounted for in presenting the data summaries, listings and descriptive statistical analyses. Relevant protocol deviations will be listed for all treated subjects. Any changes from planned protocol-specified analysis will be defined in the SAP and reported in the CSR. [APPENDIX 1](#) describes the relevant protocol deviations that will be programmed from the database.

7.3 Study Population

7.3.1 Subject Disposition

Subject disposition will be listed. Summary tables reflecting the number of subjects who are enrolled, who enter lead-in period, reasons for not entering the lead-in period, who are randomized, and reasons for not being randomized will be presented as overall for all enrolled subjects.

The number of subjects who complete the treatment period, who do not complete the treatment period, who continue the follow up period, who do not continue the follow up period, who complete the study and reasons for discontinuation from the treatment period study, will also be summarized for all treated subjects, as overall and by treatment.

7.3.2 Demographic Characteristics

Demographic characteristics such as gender, age, race and ethnicity will be listed for all treated subjects. Demographic characteristics will also be summarized for all treated subjects, as overall and by treatment.

7.3.3 Baseline Disease Characteristics

The following baseline disease characteristics will be summarized for all treated subjects as overall and by treatment:

- Type 2 diabetes mellitus (yes, no);
- Hepatic fat fraction (%);
- NASH CRN fibrosis staging (1, 2, 3);
- NAS(NAFLD activity score);

- Fatty liver index
- ALT levels

